	Section number	Screening (-21 to -1)	Active treatment phase (21 Days per cycle)										Post-treatment phase		
			Cycle 1		Cycle 2			Cycle 3		Subsequent Cycles				30-day	
			D2	D9	D2	D9	D21	D2	D9	D2	D9	D21	EOT (+7)		Long-term FU (±7) ^[1]
Assessment			DZ		52	D 3	D21	D2	D3		DJ	D21	` ,		
CT/MRI scan ^[12,13]	8.2	X ^[14]					X ^[12]					X ^[12]	X ^[15]		X ^[1]
Bone scan	8.2	X[14, 16]													
12-lead ECG ^[2]	9.8	Х	Х	Х	X [17]	X ^[17]		X ^[17]	X ^[17]	X ^[17]	X ^[17]		Х		
Document date and results of last tumor biopsy/fresh tumor biopsy	11.2.1	Х													
Blood for exploratory biomarkers in all patients ^[18]	11.2.2		Х	х				Х	х						
Confirmation of eligibility and randomization	5.1 & 5.2		Х												
Eribulin treatment ^[19]	6.1		Х	Х	Х	Х		Х	Х	Х	Х				
Document reason for treatment discontinuation	-												Х		
Survival status, PD monitoring, all anticancer medicines received	7.8														Х
For patients at selected sites															
Optional tumor biopsy ^[20]	11.2.1	Х				Х							Х		
Blood for other exploratory biomarkers	11.2.2		Х			X ^[21]		Х					Х		

AE: adverse event; RI: magnetic resonance imaging; RECIST: Response Evaluation Criteria In Solid Tumors; SAE: serious adverse event. Footnotes:

1. Regardless of treatment arm, patients discontinued from study medication for any reason, in the absence of PD, will undergo repeat imaging and tumor response assessments (including CT/MRI scans) every 8 weeks ±7 days (every 12 weeks ±7 days if the patient has been on the study for ≥1 year) until PD is documented as per RECIST v1.1, or death occurs, or the patient is lost to follow-up, or the patient withdraws consent (whichever occurs first). Once PD is recorded, the patient will be followed every 6 months (or more frequently) for Survival Follow-up only, until the patient dies, withdraws consent, or is lost to follow-up (whichever occurs first). Survival follow-up can be conducted by telephone.

CONFIDENTIAL Page 39 of 155

Protocol No.: POL6326-009

Version 3.0

2. Additional assessments to those scheduled for this study should be performed as indicated at the Investigator's discretion (e.g. due to concerns about patient safety, patient's clinical status); the findings of an unscheduled examination should be recorded in the patient's source data and eCRF.

- 3. Standard, complete physical examination.
- 4. Targeted physical examination.
- 5. Height will be measured at Screening only.

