- Randomization: Patients will be randomized within 21 days of starting screening and after having completed the required screening assessments. Patients will be randomized either to the balixafortide + eribulin treatment arm or to the eribulin treatment arm. All patients must begin treatment within 3 days after randomization.
- Treatment Phase: The treatment regimens for the study are described in Section 6.1.1. Patients will receive 21-day cycles of treatment. All patients will receive eribulin on Days 2 and 9 of each cycle (the rational for this frequency is explained in Section 3.2). In addition, patients randomized to the balixafortide + eribulin arm will receive balixafortide on Days 1–3 and Days 8–10 of each cycle.

Response Assessments During Treatment: From the date of randomization, patients will be evaluated according to RECIST v1.1 for complete response (CR), partial response (PR), stable disease (SD), or progressive disease (PD) based on CT/MRI scans performed every 6 weeks (±7 days) during the first year, and then performed every 12 weeks (±7 days), thereafter, until PD is documented by RECIST v1.1. At the discretion of the Investigator, additional radiographic tumor assessments may be done at any time if there is clinical suspicion of disease progression. The decision about the patient's disease status and progression during the study will be taken based on the local radiologist's/Investigator's assessment.

Protocol No.: POL6326-009

Version 3.0

From the date of randomization, additional bone scans will be performed at the discretion of the Investigator (e.g. to confirm CR, to follow up existing metastases, or if [based on signs and symptoms] new bone metastases are suspected).

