8.1 Independent Review of Disease Response

A blinded IRC will perform a retrospective review of radiographic images and clinical information collected on-study to verify the protocol defined endpoints of disease response and progression as assessed by the Investigator.

It is important that all specified imaging studies and clinical information (including photographs) are forwarded to the IRC as each patient enrolls and progresses through the study.

Protocol No.: POL6326-009

Version 3.0

Information on materials to be forwarded to the IRC, correct procedures for the coding/blinding of the patient's name/identity, and the return of the source data/documents to the site is provided in the imaging plan.

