The local Investigator will assess the presence of disease following CT/MRI scan performed at Screening, and those performed subsequently, and record the details in the patient's source data and eCRF relative to the previous assessment of disease status/metastatic burden.

Following initial documentation of an objective response, a confirmatory CT/MRI scan will be performed at least 4 weeks later.

Patients will continue treatment as assigned at randomization until objective PD (according to RECIST v1.1) is documented, there is unacceptable toxicity, death occurs, the patient withdraws consent, or the patient is lost to follow-up (whichever occurs first).

CT/MRI will be performed at the EoT visit in patients who are discontinued from study medication in the absence of PD; however, patients who have already demonstrated objective PD according to RECIST v 1.1 do not need to have scans repeated at the EoT visit.

Regardless of regimen, patients who are discontinued from study medication for any reason in the absence of PD, will also undergo repeat imaging and tumor response assessments (including CT/MRI scans) every 8 weeks ±7 days (every 12 weeks [±7 days] if the patient has been on the study for ≥1 year), until PD is documented as per RECIST v1.1, or death occurs, or patient is lost to follow-up, or the patient withdraws consent (whichever occurs first). If a patient stops study medication and begins another anti-cancer therapy before PD is documented, every effort should be made to perform tumor evaluation in these patients until disease progression. Every effort should be made to collect and record all anti-cancer medicines that the patient receives during Long-term Follow-up in the patient's source data and eCRF until the end of the study.

a. `Non-CR/Non-PD' is preferred over `stable disease' for non-target disease because SD is used as an endpoint for assessment of efficacy so to assign this category when no lesions can be measured is not advised.

Protocol No.: POL6326-009

Version 3.0

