8.1.1. Progression-Free Survival

PFS, as assessed by the IRC, is a co-primary efficacy endpoint in the 3^{rd} line+ population. The RECIST v1.1 guidelines will be used to determine disease progression. The alpha allocation will be 0.040 2-sided. From the date of randomization, patients will be evaluated for PD based on blinded, central review of CT/MRI scans as described in Section 8. Patients who discontinue study treatment prior to PD will undergo repeat CT/MRI scans and tumor response assessments every 8 weeks (\pm 7 days) for the first year post randomization and 12 weeks (\pm 7 days) after the first year post randomization, regardless of regimen, until confirmed PD is documented, death occurs, patient is lost to follow-up, or the patient withdraws consent (whichever occurs first).

Date of Progression will be the date assessed by the IRC.

PFS is defined as the time from the date of randomization to the earliest evidence of documented PD or death from any cause. Patients who are alive without documented PD or are either lost to follow-up or withdrew consent, will be censored at the date of last tumor assessment without disease progression.

The duration of PFS will be calculated as follows:

- For patients who have PD or died, Duration of PFS = Date of death/PD Date of randomization + 1 day;
- For patients who are alive without documented PD, Duration of PFS = Date of last tumor assessment (where response is not missing or unable to evaluate) Date of randomization + 1 day.

Table 1 below specifies the date of disease progression or censoring rules that will be carried out for the PFS analysis on the ITT (3rd line+) set:

Situation	Date of Disease Progression or Censoring	Outcome
No post-baseline assessments for tumor response and no death within first two tumor assessments	Date of randomization	Censored
Disease progression or death after two or more consecutive missed tumor response assessments	Date of last scan for tumor assessment showing no evidence of disease progression that is before the first missed visit	Censored
Not known to have progressed or died according to data in the database as of data-cut-off	Date of last scan for tumor assessment showing no evidence of disease progression	Censored
Disease progression reported on multiple response assessments	Earliest Date of Progression	Progressed
Disease progression or death after one missed tumor response assessment	Earliest Date of Progression	Progressed
Death without PD	Date of death	Progressed

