Starting anti-cancer therapy prior to observing PD or in absence of PD	Date of last scan for tumor assessment showing no evidence of disease progression prior to start date of the anti-cancer therapy	Censored

Table 1 - Date of Progression or Censoring for Progression-free Survival

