8.1.3.1. Sensitivity Analysis for PFS

A sensitivity analysis will be conducted for PFS, as assessed by the IRC on the ITT (3rd line+) set. The calculation of PFS is the same as described in section 8.1.1 where patients will not be censored at the start of a new anti-cancer therapy prior to observing documented PD. The same statistical analysis methods: Kaplan-Meier analysis, Cox proportional hazards model and supportive analysis using a stratified log-rank test will be used to estimate the effect of treatment irrespective of starting a new anti-cancer therapy.

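### Imaging ends at the open-label investigator's PD, but co-primary PFS needs PD by the blinded IRC; patients with investigator PD and no IRC PD are usually censored informatively, and no planned IRC-PFS analysis tests this

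*Protocol*

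**What the plan says.** **Who ends imaging.** Protocol 3.3 has scans continue until RECIST v1.1 PD and makes that call local: "The decision about the patient's disease status and progression during the study will be taken based on the local radiologist's/Investigator's assessment". The trial is open-label. Footnote 1 of the schedule tables (Protocol 1.1) then says: "Once PD is recorded, the patient will be followed every 6 months (or more frequently) for Survival Follow-up only".

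**Who is still scanned after stopping treatment.** Protocol 8.2.2 limits this to patients stopped without PD: "patients who are discontinued from study medication for any reason in the absence of PD, will also undergo repeat imaging and tumor response assessments". The instruction to make every effort to keep scanning after new therapy (Protocol 7.8.1) sits inside the same follow-up, so it does not reach a patient with investigator PD.

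**Whose reading defines PFS.** Protocol 8.1: "A blinded IRC will perform a retrospective review of radiographic images and clinical information collected on-study". SAP 8.1.1: "Date of Progression will be the date assessed by the IRC".

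**How a patient without IRC PD is censored.** SAP Table 1 has two relevant rows. One covers patients described as "Not known to have progressed or died according to data in the database as of data-cut-off" and censors them at the last scan without progression. The other covers new anti-cancer therapy before PD and censors at the "Date of last scan for tumor assessment showing no evidence of disease progression prior to start date of the anti-cancer therapy".

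**What is planned around it.** SAP 8.1.3.1 repeats the IRC analysis without censoring at new therapy, "to estimate the effect of treatment irrespective of starting a new anti-cancer therapy". Investigator-assessed PFS is a secondary, supportive analysis (SAP 8.4.1). The censoring reasons in SAP 8.1.3 include no separate line for investigator PD without IRC PD, and no discordance table is described.

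**The concern.** Protocol 3.1 introduces blinded central review to remove assessment bias and allow an unbiased effect estimate. Under the follow-up rules, however, the unblinded investigator decides when the IRC stops receiving scans. A local PD call is a sign of worsening disease, so censoring at that point is related to the patient's near-term risk of progression. The Cox model treats it as unrelated.

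Two things are at stake. The first is the number of IRC events. The second is the co-primary hazard ratio, if investigators call PD early more often in one arm than in the other, which is possible when they know the treatment. Nothing in the planned output would show whether this had happened.

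**Working it through.** **1. One patient under the rules.** The investigator calls PD at week 12; the IRC reads the same scan as not progressed.

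- Under the Protocol 1.1 footnotes, follow-up is now for survival only, so no later scan reaches the IRC.
- If the patient starts another therapy, the SAP Table 1 new-therapy row censors at the last progression-free scan before it.
- If not, the last-scan row censors at week 12.
- Two exceptions. A patient who dies without new therapy before two assessments are missed counts as an event. A patient kept on study drug after local PD gets a further scan at least 6 weeks later (Protocol 3.3, 8.2.2).

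**2. The plan's event count.** Inputs from SAP 4.1 and Protocol 12.3.1: hazard ratio 0.674, 1-sided alpha 0.02, power 90%, 1:1 allocation. Schoenfeld:

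D = 4(z0.98 + z0.90)² / (ln 0.674)² = 4(2.054 + 1.282)² / 0.1557 ≈ 286.

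This reproduces the stated figure, which is not in question.

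**3. Room for lost events.** 320 − 286 = 34 patients, or 10.6%, may be without an IRC event. Above that share, 286 IRC events cannot be reached at any length of follow-up. The corresponding figure in the Overall Population is 384 − 346 = 38 (9.9%). Neither sample-size section states an allowance for lost events.

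**4. Illustrative effect on the hazard ratio.**

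- From the documents: 160 patients per arm, control median 3.9 months, hazard ratio 0.674, non-linear accrual over 12 months (η = 2), cut-off at month 24, 6-weekly scans in year one and 12-weekly after.
- Assumed: exponential PFS; a given share of patients has local PD called one scan before the IRC would detect it, and is censored at that earlier scan; no deaths or other losses.
- Analysis: Cox model with treatment only, Efron ties, 2,000 simulated trials per row, 1-sided 0.02.

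| Early local calls, control / combination | Mean IRC events by month 24 | Hazard ratio | Power |
|---|---|---|---|
| 0% / 0% | 277 | 0.67 | 89% |
| 10% / 10% | 249 | 0.68 | 85% |
| 20% / 20% | 221 | 0.67 | 81% |
| 20% / 10% | 234 | 0.74 | 58% |
| 10% / 20% | 236 | 0.60 | 97% |

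Variants of this set-up gave 0.73 to 0.74 for 20%/10%, with power of 58% to 65%. In a continuous-time version, letting 20% of the discordant patients still count as events (early death) moved 0.74 to 0.72 and 0.60 to 0.62, so the bias shrinks but remains. The 97% in the last row is a product of the bias. With no true effect, the same 10%/20% split gives a hazard ratio of about 0.91 and a 1-sided error of about 10% instead of 2%.

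Tie handling matters on a 6-week grid. Breslow ties give about 0.70 and 84% with no discordance at all, so that attenuation must not be attributed to censoring.

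**5. Do the planned analyses address it?** SAP 8.1.3.1 lifts the new-therapy censoring but cannot use scans that were never taken. Investigator PFS counts the early calls as events, but it replaces the IRC reading for every patient and so does not isolate the discordant group.

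**The case against.** **The protocol discourages premature PD calls.** Protocol Appendix 3 asks for follow-up of equivocal new lesions, allows treatment to the next assessment when progression is equivocal, and treats a modest non-target increase as usually insufficient. Treatment beyond PD is allowed, and if progression is not confirmed, scanning resumes on schedule. This stands: it should reduce discordance. It does not reach the patient who stops at local PD and starts another therapy.

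**The imaging plan is not available.** It may contain a real-time central read. SAP 8.1.1 speaks of central review and of scanning until PD is confirmed, which is compatible with that. But that sentence concerns patients who stop treatment before PD, and neither document describes central feedback to sites. If such a step exists, the protocol should say so.

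**Investigator PFS is already planned with the same model.** A large gap between the two PFS results would be a warning. It would not show which patients caused it, or in which arm.

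**These patients do have a censoring label.** Many would be reported as having started new therapy. That is correct, so the complaint is not that they go uncounted but that they are indistinguishable from other patients under that label.

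**Continued imaging.** A reader might infer that scanning to IRC PD would restore the planned hazard ratio and power in the primary analysis. The documents do not support this. The new-therapy row of SAP Table 1 censors these patients whether or not later scans exist, so for those who start another therapy the extra scans would inform only SAP 8.1.3.1.

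**Conclusion.** The point holds as a gap in the planned analyses. Investigator PD without IRC PD leads in most cases to informative censoring of the co-primary endpoint, and no planned IRC-PFS analysis tests its effect. The same mechanism applies to PFS in the Overall Population.

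Equal discordance leaves the hazard ratio close to its true value and costs events and some power. Unequal discordance biases it against the combination if early local calls are commoner on control, and in its favour if they are commoner on the combination. The 34-patient margin follows from the plan's own figures. The hazard ratios of about 0.73-0.74 and 0.60 rest on assumed discordance rates and an assumed one-scan lead.

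A reader might infer that the result will be biased, or in a known direction. The documents support neither: they give no discordance rate and no evidence that it differs by arm. The recommendation is a low-cost improvement.

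**What to change.** **SAP 8.1.3.1.** Add an IRC-PFS sensitivity analysis in which investigator PD without IRC PD counts as an event at the date of that scan. State that it overrides both the last-scan and the new-therapy censoring rows of Table 1 for these patients. Use the same Cox model and log-rank test as the primary analysis.

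**SAP 8.1.3.** Add investigator PD without IRC PD as a separate censoring reason, and tabulate by arm how often the investigator's PD is earlier than, the same as, or later than the IRC's.

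**Cost.** SAP wording and a little programming, on data already collected. The composite analysis admits some unblinded assessments, so it should remain a sensitivity analysis.

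**Optional.** Scanning to IRC PD would need a protocol amendment, prospective IRC reads returned to sites, and extra scans in discordant patients, some already on other therapy. It would inform the primary estimate only if reconciled with the new-therapy row of SAP Table 1, and is not needed for the two changes above.

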3.4 Randomization and Treatment Allocation

Patients will be randomized in a 1:1 ratio to one of the following treatment regimens:

Balixafortide + eribulin treatment arm

or

Eribulin treatment arm.

Patients will be stratified as described in Section 3.3. CXCR4 expression (high versus low; threshold to be determined) is not currently planned as a stratification factor since (i) there is currently no validated test, and (ii) there was no correlation of ORR/CBR with level of CXCR4 expression in the Phase 1 trial. That said, CXCR4 expression level, based on immunohistochemistry (IHC) of historical tumor samples, will be recorded and the correlation

Sponsor Logo/Name: Polyphor Ltd

Protocol No.: POL6326-009

Version 3.0

with efficacy will be explored. It should be noted that all BC patients screened for the Phase 1 trial expressed CXCR4 to some degree.

Both the randomization and the stratification will be handled by an Interactive Response System (IRT); refer to the IRT manual for further details.

4. STUDY OBJECTIVES AND ENDPOINTS

4.1 Primary Objective

The primary objective of this study is:

• To evaluate the efficacy of balixafortide + eribulin versus eribulin monotherapy on (i) PFS in the Overall Population and (ii) PFS and ORR in the 3rd line + population.

4.2 Secondary Objectives

The secondary objectives of this study are:

- To compare the OS between patients in the balixafortide + eribulin treatment arm versus eribulin monotherapy treatment arm.
- To compare measures of tumor response between patients in the balixafortide + eribulin treatment arm versus eribulin monotherapy treatment arm.
- To evaluate the safety and tolerability of balixafortide + eribulin versus eribulin monotherapy.

4.3 Exploratory Objectives

The exploratory objectives of this study are:

- To determine whether the treatment outcome correlates with baseline ER, PgR, or CXCR4 expression level.
- To assess tumor tissue and circulating biomarkers and possible association with patient treatment outcome.
- To explore immune response as assessed by iRECIST.
- Measurement of plasma concentration of balixafortide and potential metabolites to integrate in a population PK model.
- To assess the QoL as reported by patients in the balixafortide + eribulin treatment arm versus eribulin monotherapy treatment arm using standard QoL assessments.

4.4 Endpoints

4.4.1 Overall Population Efficacy Endpoints

Primary Efficacy Endpoint

In the Overall Population intended for regulatory submissions in the EU and jurisdictions in which the 2nd line + eribulin label applies, the primary endpoint is:

Date: 15 July 2019

Protocol No.: POL6326-009

Version 3.0

PFS according to RECIST v1.1 guidelines, as assessed by the IRC.

Key Secondary Efficacy Endpoint

OS.

The statistical design in the overall, 2nd line+ population, with pre-defined alpha allocation and recycling, is such that if PFS does not meet statistical significance at its allocated alpha level, then the design still allows OS to be tested and, if it meets statistical significance at its allocated alpha level, then the study can still be formally positive for efficacy.

Other Secondary Efficacy Endpoints

- PFS according to RECIST v1.1 guidelines, as assessed by the local Investigator's review.
- ORR [confirmed CR + confirmed PR]) according to RECIST v1.1 guidelines, as assessed by the IRC in the Overall Population.
- ORR (confirmed CR + confirmed PR) according to RECIST v1.1 guidelines, as assessed by the local Investigator's review.
- CBR (proportion of patients with confirmed CR, confirmed PR, or SD ≥6 months) according to RECIST v1.1 guidelines as assessed by the IRC and by the local Investigator's review.
- Disease control rate (DCR; number of patients with confirmed CR, confirmed PR, or SD) according to RECIST v1.1 guidelines as assessed by the IRC and by the local Investigator's review.
- Time to response as assessed by the IRC and by the local Investigator's review.
- Duration of response as assessed by the IRC and by the local Investigator's review.

4.4.2 3rd Line + Population Efficacy Endpoints

Co-Primary Endpoints

In the 3rd line + population intended for regulatory submissions in the US and jurisdictions on which the 3rd line + eribulin label applies, the co-primary endpoints are:

- ORR (confirmed CR + confirmed PR) according to RECIST v1.1 guidelines, as assessed by the IRC.
- PFS according to RECIST v1.1 guidelines, as assessed by the IRC.

If PFS in the 3rd line + population is met at the allocated alpha level, PFS in the Overall Population will also be formally tested at the same alpha level.

Key Secondary Efficacy Endpoint

OS.

Protocol No.: POL6326-009

Version 3.0

The statistical design in the 3rd line + population, with pre-defined alpha allocation and recycling, is such that even if ORR does not meet statistical significance at its allocated alpha level, then PFS can still be tested and, if it meets statistical significance at its allocated alpha level, the study can still meet its primary objective. Further, if PFS does not meet statistical significance at its allocated alpha level, then OS can still be tested and, if it meets statistical significance at its allocated alpha level, then the study can still be formally positive for efficacy.

Other Secondary Efficacy Endpoints

- PFS according to RECIST v1.1 guidelines, as assessed by the local Investigator's review.
- ORR (confirmed CR + confirmed PR) according to RECIST v1.1 guidelines, as assessed by the local Investigator's review.
- CBR (proportion of patients with confirmed CR, confirmed PR, or SD ≥6 months) according to RECIST v1.1 guidelines as assessed by the IRC and by the local Investigator's review.
- DCR (number of patients with confirmed CR, confirmed PR, or SD) according to RECIST v1.1 guidelines as assessed by the IRC and by the local Investigator's review.
- Time to response as assessed by the IRC and by the local Investigator's review.
- Duration of response as assessed by the IRC and by the local Investigator's review.

